#### 4. ANALYSIS SETS

Primary RCT analyses will be intent-to-treat.

## **5. STATISTICAL ANALYSES AND DESCRIPTION OF MAIN TABLES**

**AIM 1a:** The proportion of all women enrolled in the study who use PrEP (proportion of women exposed to PrEP) will be compared between trial arms using GEE with a binomial link.

**AIM 1b:** The proportion with 'appropriate' use will be compared between arms using GEE with a binomial link. PrEP adherence will be measured among women on PrEP using DBS TFV drug levels. All women receiving PrEP will have 3-monthly DBS samples available. For each trial arm (10 clinic-cluster) a random subset of 220 DBS will be assessed. TFV drug levels will be compared by trial arm using GEE with a Gaussian link. PrEP duration will be computed for each woman based on self-report and pharmacy records and average duration compared between arms using GEE with a Gaussian link. Reported and confirmed partner with HIV status, proportions of partner HIV positive, unknown and HIV negative status, and reported and confirmed partner ART use will be compared between arms using GEE with a binomial link.

Infant outcomes: mean birthweight and serial weight-for-age z-scores (WAZ), height-for-age z-scores (HAZ), and weight-for-height z-scores (WHZ) will be compared between trial arms using GEE with a Gaussian link. A separate analysis will assess birth and infant outcomes by PrEP exposure in the combined arms.

**AIMS 2-4** will be conducted after the primary analysis and will not be reviewed by the EAC.

---

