AIM 1a. In a cluster-RCT, compare universal PrEP (offer to all; women self-select PrEP) to targeted PrEP (limit the offer to women identified as high risk through a standardized risk assessment and partner self-testing) for outcomes reflecting the balance of PrEP effectiveness and avoiding unnecessary PrEP exposure to women at low or no risk of HIV: HIV incidence at 9 months postpartum among all women (including those who did and did not receive PrEP) and proportion of women exposed to PrEP.

AIM 1b. To compare trial arms for proportion of women ‘appropriately’ on PrEP (risk factors), PrEP adherence (drug levels) and duration, partners with known HIV status, partners on ART; infant outcomes (growth, birth outcomes, HIV status).

AIM 2. To estimate the incremental cost-effectiveness of targeted PrEP compared to universal PrEP for women during pregnancy and postpartum, per HIV infection and disability-adjusted life-year (DALY) averted.

AIM 3. To qualitatively assess barriers and facilitators to uptake, adherence, acceptability, and feasibility in universal and targeted PrEP models at the organizational, provider, and individual woman level.

7) BACKGROUND

In this study we aim to compare two models of PrEP delivery in pregnant women – universal PrEP (offered to all women, women self-select) or targeted PrEP (partner HIV self-test combined with risk score to determine whether PrEP is offered). In a cluster-RCT we will compare 10 clinics randomized to universal and 10 to targeted (at least 200 women per clinic) and compare HIV incidence among all enrolled women (including those on and not on PrEP) at 9 months postpartum and the proportion of women who take PrEP. We hypothesize that PrEP can be implemented in antenatal care clinics in way that will be acceptable and used by women at risk of HIV acquisition during pregnancy. Our also hypothesize is that a targeted approach will be more specific, effective, and cost-effective – maximizing PrEP use among pregnant women at risk and minimizing PrEP use for women without risk – thus providing the best balancing of effectiveness, cost-effectiveness, and potential for unneeded medication exposure.

a) LITERATURE REVIEW

HIV Acquisition in Pregnancy and Postpartum

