During the past decade, legal, ethical, and policy deliberations have informed a vision to accelerate access to effective interventions for pregnant women and their children (64). Pregnant women currently receive several preventive interventions, including anti-malarials, PMTCT, and TB-prevention (if HIV infected). For some interventions (malaria prophylaxis and early PMTCT), pregnancy implementation was informed by RCTs conducted in pregnant women and their infants with most benefits for the infant. For other interventions (isoniazid in HIV-infected women), efficacy evidence was extrapolated from non-pregnant adult studies and safety data was obtained from observational studies. The level of safety evidence for PrEP (no animal fetal toxicity, thousands of infants exposed to TDF/FTC PMTCT, hundreds to PrEP in early pregnancy) led WHO, CDC, and the Kenyan Ministry of Health (MoH) to permit PrEP use in pregnancy (61, 65, 66). WHO early-release guidelines (Sept 2015) recommend PrEP for anyone at 'substantial HIV risk', and noted need for research on PrEP in pregnancy and lactation (66), and updated WHO guidance from 2017 recommended the use of PrEP in pregnancy and lactation, although important safety and implementation gaps remain. Implementation science studies can provide a framework to increase accrual of safety and effectiveness data of PrEP in pregnancy while refining programmatic strategies.

8) RATIONALE

In a region with 15-20% HIV prevalence, an estimated 20% of HIV-uninfected women could have HIV exposures in pregnancy. In a theoretical scenario of perfect PrEP coverage, all women at risk receive PrEP while no women not at HIV risk receive PrEP (Figure 4). With mandatory PrEP

[figure not shown]

Figure 4: Potential PrEP in pregnancy, delivery strategies. Measuring uptake, process, and HIV incidence, we can inform the best health systems model for PrEP delivery in pregnancy.

given to all women (similar to the approaches used for malaria prophylaxis), all women at risk would be covered but many women not at risk receive unnecessary PrEP. Our premise is that a targeted PrEP model may be closer to perfect coverage than a universal offer/self-select model. Implementing targeted PrEP through strategies that include facilitation of partner testing with self-tests could add HIV prevention benefit by increasing partner HIV diagnosis and treatment similar to the initiation of PrEP among pregnant women. By implementing these strategies and

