coefficient of variation (k) of 0.2, the study has 80% power to detect a 2-fold difference in HIV incidence (between 4% and 2%) with 10 clinics per cluster and at least 200 women per cluster (Table 3). If targeted PrEP resulted in much better performance (67% decrease rather than 50%), 6 clinics per cluster would be sufficient. Deriving our sample size from HIV incidence difference is conservative and will enable ample statistical power to detect effects on other outcomes (such as proportion on PrEP and partner characteristics). Table 4 outlines implications of potential RCT outcomes illustrating the value of data regarding the two PrEP delivery models in scenarios with

or without a significant difference in HIV incidence. We anticipate that the targeted arm may have 20% of women receiving PrEP (based on MSS risk score estimates) while the universal PrEP arm may have 5-25% of women requesting PrEP, however, these are speculative estimates. The study may not detect a difference in HIV incidence between PrEP delivery models because of appropriate PrEP uptake and use in both. However, as outlined in the contingency table (Table 4), for all scenarios the RCT would yield important data on viable approaches for delivering PrEP in pregnancy and likely reveal a superior model in terms of the balance of effectiveness, safety, acceptability, feasibility, and cost-effectiveness.

Table 4: Contingency Table Demonstrating Implications of Potential RCT Outcomes				
	Potential HIV incidence outcome	Other potential results	Impact on programs policy in high HIV prevalence regions	Programmatically relevant data from study
Hypothesis Proved	Targeted better	Fewer women on PrEP, cost-effective, safe	Implement targeted PrEP	Data to model and compare impact on HIV transmission, cost, and scale up.
Hypothesis opposed	Universal better	Fewer women on PrEP, cost-effective, safe	Implement universal PrEP	
Mixed benefits	Universal better	Universal too many women on PrEP not cost effective	Refine universal strategy to decrease cost and unnecessary PrEP exposure	HIV incidence/CI, cost-effectiveness, safety, feasibility, process
Mixed findings	Incidence low in both, no difference	Targeted more cost-effective results in few on PrEP	Implement targeted PrEP	HIV incidence estimate/CI, cost-effectiveness, safety, process
		University more cost-effective and fewer women on PrEP	Implement universal PrEP	

d) RECRUITMENT PROCEDURES

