 - Demographic information (education, obstetric history, marital status, income)
 - Risk Perception Assessment
 - Risk Score Card
 - Partner HIV status
 - Self-Efficacy
 - Social Support and Mental Health
 - IPV assessment
 - Partner Characteristic
 - PrEP attitudes and acceptability (HIV/PrEP Stigma Assessment)
- ANC Card Abstraction form
 - HIV status
 - Gestational Age
 - Maternal Age
 - Syphilis
 - TB status
- PrEP Counseling Outcomes form
- Partner self-test results
- MCH Card Abstraction Form, including:
 - Infant length
 - Birth weight
 - Gestational age at birth
 - Serial growth
 - Stillbirth
 - Neonatal mortality
 - Miscarriage
 - Infant congenital abnormality
- Infant, neonatal and maternal mortality (including WHO verbal autopsy instrument)
- Maternal follow up
 - HIV-status 6-weeks postpartum
 - 14 weeks postpartum
 - 6-months postpartum
 - HIV-status 9 months postpartum
 - Hepatitis B Antigen test result
 - Creatinine level test result
 - Sexual activity and contraceptive use
- PrEP Adherence
 - Pill Count data

- Self-Assessment
- DBS collection methods
- Discontinuation Documentation
- Health Economic Evaluation
 - Incremental costs at facility level, including costs incurred and averted
 - Costs incurred at participant level interview form
 - Time and motion data collection form

h) VARIABLES: Outcomes, indicators, and source documents

Table 7: Variables: Outcomes, Indicators, and source documents		
	Indicator	Source
Primary Outcomes		
Maternal HIV, 6-weeks pp	HIV Rapid Test	Study Visit, maternal specimens
Maternal HIV, 9-months pp	HIV Rapid Test	Study Visit, maternal specimens
PrEP Exposure	Number received PrEP/All Participants	PrEP Counseling outcome form
Secondary Outcomes		
Appropriate PrEP Use	Scored 1 for high risk women using PrEP and low risk women not using PrEP; 0 for high risk women NOT on PrEP and low risk women using PrEP	PrEP Counseling outcome form
PrEP Adherence	TFV/DP and FTC test results from 440 randomly selected specimens	Dried Blood Spots
PrEP Duration	Number of days on PrEP	Self-report captured on adherence counseling form; pharmacy records
Partners HIV Self-test	Partners Self-test result	self-report
Infant Birth weight	Birth weight	MCH card
Preterm Birth	Estimated gestational age at birth	MCH card
Infant Growth	Infant height, weight, and age for WAZ, HAZ, and WHZ Z-scores	MCH card
Cost Effectiveness Analysis Outcomes		

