## **3. SAMPLE SIZE CONSIDERATIONS**

Restricted randomization will be used to balance the two arms of the trial in terms of prevalence of HIV, ANC volume, and rates of partner disclosure at included clinics (based on data from our prior CHIME evaluation of 141 MCH clinics). Assuming a coefficient of variation (k) of 0.2, the study has 80% power to detect a 2-fold difference in HIV incidence (between 4% and 2%) with 10 clinics per cluster and 200 women per cluster (Table 1). If targeted PrEP resulted in much better performance (67% decrease rather than 50%), 6 clinics per cluster would be sufficient. Deriving our sample size from HIV incidence difference is conservative and will enable ample statistical power to detect effects on other outcomes (such as proportion on PrEP and partner characteristics). Table 2 outlines implications of potential RCT outcomes illustrating the value of data regarding the two PrEP delivery models in scenarios with or without a significant difference in HIV incidence. We anticipate that the targeted arm may have 20% of women receiving PrEP (based on MSS risk score estimates) while the universal PrEP arm may have 5-25% of women requesting PrEP, however, these are speculative estimates. The study may not detect a difference in HIV incidence between PrEP delivery models because of appropriate PrEP uptake and use in both. However, as outlined in the contingency table (Table 2), for all scenarios the RCT would yield important data on viable approaches for delivering PrEP in pregnancy and likely

reveal a superior model in terms of the balance of effectiveness, safety, acceptability, feasibility, and cost-effectiveness.

k	HIV incidence universal	HIV incidence targeted	# women per clinic	#clinics per arm	Total # women
0.2	4%	2%	50	27	2700
0.2	4%	2%	100	15	3000
0.2	4%	2%	150	12	3600
0.2	4%	2%	200	10	4000
0.2	4%	2%	250	9	4500
0.2	4%	2%	300	8	4800
0.2	4%	1.3%	200	6	2400

	Potential HIV incidence outcome	Other potential results	Impact on programs policy in high HIV prevalence regions	Programmatically relevant data from study
Hypothesis Proved	Targeted better	Fewer women on PrEP, cost-effective, safe	Implement targeted PrEP	Data to model and compare impact on HIV transmission, cost, and scale up.
Hypothesis opposed	Universal better	Fewer women on PrEP, cost-effective, safe	Implement universal PrEP	

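### The Aim 1a exposure outcome counts PrEP use in all women, so it cannot by itself show whether PrEP was avoided in women at low or no risk, and the contingency table reads its direction as if it could.

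*SAP*

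**What the plan says.** The protocol (section 6, Aim 1a, and again in section 9) describes the aim as comparing the arms on "outcomes reflecting the balance of PrEP effectiveness and avoiding unnecessary PrEP exposure to women at low or no risk of HIV". It then names two outcomes: HIV incidence at 9 months postpartum and the proportion of women exposed to PrEP.

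Protocol Table 7 lists PrEP exposure as a primary outcome with the indicator "Number received PrEP/All Participants". Under Aim 1a, SAP section 5 carries this into the analysis: "The proportion of all women enrolled in the study who use PrEP (proportion of women exposed to PrEP) will be compared between trial arms", by GEE. Neither place conditions on risk.

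In protocol Table 4, and the matching table in SAP section 3, the row where the study hypothesis is proved pairs better incidence in the targeted arm with "Fewer women on PrEP, cost-effective, safe". Other rows also treat fewer on PrEP as a plus, or too many on PrEP as a drawback. No row covers lower incidence in the targeted arm with more women on PrEP.

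Three figures bear on direction. The protocol Rationale says "an estimated 20% of HIV-uninfected women could have HIV exposures in pregnancy". The sample size sections expect 20% on PrEP in the targeted arm. They also say "the universal PrEP arm may have 5-25% of women requesting PrEP, however, these are speculative estimates".

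A risk-conditional outcome, appropriate use, is also planned. It scores a success for a high-risk woman on PrEP or a low-risk woman not on it. SAP section 2 lists it as primary and PrEP uptake as secondary. Protocol Table 7 and SAP shell Table 2 rank them the other way round.

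**The concern.** The aim concerns one subgroup, women at low or no risk, but the outcome sums over everyone. Two arms with the same total can differ completely in who took PrEP. An arm that reaches exactly the women at risk can also show more PrEP use than an arm that reaches few of them.

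The contingency table makes this matter, because it attaches policy conclusions to the total. If targeting works and universal uptake is modest, a reader using that table would find the exposure result on the wrong side, and no row that describes what happened. The trial would then report a clear difference in exposure that does not answer the question the aim poses.

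**Working it through.** **Inputs.** At-risk share 20% (protocol, Rationale). PrEP use 20% targeted and 5-25% universal (sample size sections). Score above 6: 16% of women (protocol, Background, description of the risk tool). 2,000 women per arm, 10 clinics of 200, k = 0.2 (SAP sections 1 and 3).

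**1. The plan's own benchmark.** The Rationale describes perfect coverage as all at-risk women on PrEP and nobody else. With 20% at risk, that is 20% of all women, the figure expected in the targeted arm.

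**2. Total against unnecessary use.** Assume perfect targeting: 400 of 2,000 on PrEP, none low risk. Let universal uptake be U, with at-risk women r times as likely to take PrEP. Low-risk uptake is U/(0.8 + 0.2r). Low-risk users per arm are 2,000 × 0.8 × that rate.

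| U | Total, targeted minus universal | Low-risk users in universal, r = 1 | r = 4 |
|---|---|---|---|
| 5% | +15 points | 80 | 50 |
| 10% | +10 | 160 | 100 |
| 15% | +5 | 240 | 150 |
| 20% | 0 | 320 | 200 |
| 25% | −5 | 400 | 250 |

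Low-risk use favours the targeted arm (0 users) in every row. The total, read with fewer as better, goes against it from 5% to just under 20% (15 of the 20 points of the range), is neutral at 20%, and favours it above. If perfect targeting means 16% on PrEP instead, the adverse part is 5-16%, or 11 of 20 points.

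**3. What appropriate use shows.** With 20% at risk the score is 0.2 × (high-risk uptake) + 0.8 × (1 − low-risk uptake). Nobody on PrEP gives 0.8 × 1 = 80%. At r = 1 the universal arm scores 0.8 − 0.6U, or 77% at U = 5% and 65% at U = 25%. At r = 4 it scores 80% at every U, the same as an arm with no PrEP, because over-use and under-use offset each other.

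**4. How far an example of unnecessary use can be pushed.** Take 20% targeted, 10% universal and 16% scoring above 6. Low-risk users in universal are 0.84 × 10% = 8.4% of all women if uptake is unrelated to risk. They are 0.84 × 0.10/(0.84 + 0.32) = 7.2% if high-risk women are twice as likely to take it. In the targeted arm they are 20 − 16u, where u is uptake among women scoring above 6. At u = 100% this is 4%. It equals 8.4% at u = (20 − 8.4)/16 = 72.5% and 7.2% at u = (20 − 7.2)/16 = 80%. At u = 60% it is 10.4%, worse than universal.

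**5. Chance of a significant difference in the total.** The documents give no power for this outcome. The sample size table does reproduce from the cluster formula for proportions, assuming two-sided 5%. For 4% against 2%, 7.85 × (0.000192 + 0.000098 + 0.00008)/0.0004 = 7.26, and adding 2 gives 9.26, so 10 clinics.

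The same variance for 20% against 10%, with 10 clinics and no small-sample allowance, gives SE = √{[0.16/200 + 0.09/200 + k²(0.04 + 0.01)]/10}.

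- k = 0.2: SE 0.0180, z = 5.5, power over 99.9%.
- k = 0.5 (assumed): SE 0.0371, z = 2.7, power about 77%.

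For 20% against 15%, replacing 0.09 by 0.1275 and 0.01 by 0.0225, power is about 71% at k = 0.2 and about 23% at k = 0.5. A small-sample allowance lowers these figures.

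**The case against.** The strongest reply is that no favourable direction is built into the outcome. SAP section 5 states a plain comparison. The protocol hypothesis speaks of an optimised proportion, not a lower one. Fewer appears only in the contingency table, which is offered as illustration and read jointly with incidence, cost and safety. This stands, and it limits the point: the outcome has no defined direction of its own, and the table supplies one that fits only part of the expected range.

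Second, SAP section 1 restates the aim as balancing effectiveness and safety, and total exposure is a legitimate quantity for safety and cost. This also stands and is a reason to keep the outcome. It does not make the total a measure of "avoiding unnecessary PrEP exposure to women at low or no risk of HIV".

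Third, appropriate use already conditions on risk, and SAP section 2 makes it primary. This stands in part. It does not isolate over-use, and its ranking is contradicted elsewhere.

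A reader might go further and infer that the outcome generally points against the targeted arm, or that unnecessary use would favour targeted about two to one while the total reads the opposite way with near-certain power. The documents do not support either. The direction reverses above 20% universal uptake. The two-to-one figure needs every woman scoring above 6 to take PrEP, whereas the protocol says these women choose whether to proceed. The power figure borrows k = 0.2, which the plan assumes for HIV incidence.

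**Conclusion.** The mismatch between aim and outcome is real and needs no modelling: a proportion over all women cannot identify use among low-risk women. The gap in the contingency table can be read directly from it.

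The size is conditional. If 20% are at risk and targeting is perfect, reading fewer as better misleads for universal uptake of 5% to just under 20%. With a 16% share it misleads for 5% to just under 16%. Perfect targeting and the uptake ratios are illustrative, and the plan calls its own uptake shares speculative. The ratio of unnecessary use between arms, and the chance of a significant result against targeting, should be quoted only as ranges under stated assumptions.

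It would be wrong to infer that the trial has no measure conditioned on risk. It has one, with the limits shown above. The remedy is cheap and should be made before analysis.

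**What to change.** - **SAP section 5 (Aim 1a) and shell Table 2.** Keep the all-women proportion, but state that it measures total exposure for safety and cost and has no favourable direction. Beside it, compare arms with the same GEE on PrEP use among low-risk women and, separately, among high-risk women. Do not replace the outcome with low-risk use alone, since an arm with nobody on PrEP would then look best.
- **Risk group.** Fix it from the enrolment data, which the protocol's enrolment procedures collect for all participants. Protocol Table 5 gives 0 points for a known partner status, including a known HIV-positive partner, so state that for this analysis such women are not classed as low risk.
- **Sensitivity analysis.** Self-testing is offered only in the targeted arm and can change what is known of the partner after enrolment. Add an analysis that handles women whose partner status changes in this way.
- **Contingency table (both documents).** Refer to fewer low-risk women on PrEP, and add the row for lower incidence in the targeted arm with more women on PrEP.
- **Outcome status.** Reconcile SAP section 2 with protocol Table 7 and shell Table 2 on which of appropriate use and PrEP exposure is primary.

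**Cost.** No new data and a little more analysis. Each stratum has a smaller denominator, about 84% of women low risk and 16% high risk by score, so the high-risk comparison is the less precise. Reconciling the primary outcome is a substantive amendment and should be documented as one.

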## 1. STUDY SUMMARY AND AIMS

**Study Purpose:** The broad objective of this study is to determine the best approach to PrEP delivery in pregnancy using existing MCH systems as a platform for efficiently delivering PrEP to pregnant women.

**Study Design:** This is a cluster randomized clinical trial with 20 ANC clinics in Western Kenya (Siaya and Homa Bay) counties comparing Universal and Targeted PrEP administration. The facility-level cluster randomization will be conducted using a restricted randomization approach based on new antenatal care clinic (ANC) volume, and County. County will be used as a proxy for County differences in HIV prevalence in the restricted randomization approach. In the Universal PrEP arm, PrEP is offered to all and women select whether they want to take it. In the Targeted PrEP arm PrEP is offered to women identified as high risk through a standardized risk assessment and partner self-testing.

**Study Population and Sites:** Twenty ANC clinics in Western Kenya (Siaya and Homa Bay) counties will be randomized, 10 Universal and 10 Targeted PrEP administration. At each clinic women attending antenatal care will be enrolled in the study. Eligibility for enrollment will include age  $\geq 15$  years, pregnancy with the gestational age up to 36 weeks by last menstrual period (LMP) or best available estimate, and tuberculosis negative, plans to reside in area for at least one year postpartum, plans to receive postnatal and infant care at the study facility, and are not currently enrolled in any other studies.

**Study Size:** At least 200 women per clinic (2,000 per ARM)

**Study Duration:** At each clinic, enrollment will occur over an approximately 10-month period (~20 HIV negative women enrolled per month) with a ~1-year period of follow-up to 9 months postpartum (time of routine measles immunizations).

**Treatment Regimen:** PrEP medication and dosing will follow the 2016 Guidelines on Use of Antiretroviral Drugs for Treating and Preventing HIV Infections in Kenya using the preferred oral TDF/FTC (300mg/200mg) once per day

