### Primary Aims:

**AIM 1a:** To compare Universal PrEP to Targeted PrEP for outcomes reflecting the balance of PrEP effectiveness and safety:

1. HIV incidence at 9 months postpartum
2. Proportion of women who accepted PrEP

**Sub-Aim 1a.** To compare infant outcomes (growth, birth outcomes, HIV status) between PrEP users and nonusers in combined trial arms.

**AIM 1b:** To compare trial arms for:

1. Proportion of women 'appropriately' on PrEP (based on risk factors)
2. PrEP adherence (DBS) and duration
3. Partners with known HIV status, on ART

**AIM 2:** Health economic evaluation of targeted vs. universal PrEP

**AIM 3:** Assessment of barriers and facilitators of PrEP delivery strategies at the individual patient, healthcare facility, and organizational level

*This analysis plan will focus on Aim 1 except for sub-aim 1a which is in a separate SAP for birth/infant outcomes.*

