### **Randomization scheme text for a randomized, unblinded study**

The facility-level cluster randomization will be conducted using a restricted randomization approach based on new antenatal care clinic (ANC) volume, and county. County will be used as a proxy for HIV prevalence.

We will select 20 clinics from Western Kenya. Ten clinics will be randomized to universal PrEP and ten to targeted PrEP (Table 2). To ensure balance between study arms in terms of key site characteristics, sites will be categorized on HIV prevalence and ANC volume, and restricted randomization will be used for site (cluster) allocation to intervention and control arms (67). Specifically, all possible randomizations that evenly distribute sites on these two specified factors (HIV prevalence, ANC volume) into 2 study arms will be generated, and one combination will be selected using a random number generator. Randomization and allocation will be performed by [name], who has no knowledge of sites other than the variables included in the restricted randomization process.

In order to build excitement for the study among study staff and facility representatives, we aim to conduct the final randomization activities as part of the study training. Prior to the training, each facility was ranked by county and ANC volume and assigned to one of six groups. The ANC volume and county for each group are summarized in Table 1.

Table 1: Summary of facility group assignments for PrIMA randomization activities			
Group	County	Number of Facilities	Mean ANC Volume (SD)
1	Homa Bay	2	173 (60.8)
2	Homa Bay	4	59.8 (1.3)
3	Homa Bay	4	53.8 (3.3)
4	Siaya	2	140 (26.9)
5	Siaya	4	54.8 (6.4)
6	Siaya	4	38 (5.5)

One representative from each facility will be identified to represent their facility during the randomization event. Representatives from facilities in each group will be asked to select a ball from a bag during the PrIMA training. The bag will contain one ball per facility, and half of the balls will be blue (universal arm) and half of the balls will be orange (targeted arm). The final facility randomization will be determined by what color ping pong ball the facility representative selects. Facility group assignments are including in Table 2.

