**Table 2. Primary and secondary endpoints**

	N (%) or incidence/100 py			RR (95% CI), p-value
	All subjects	Trial arm		
		Universal	Targeted	
Primary outcomes				
HIV incidence				
Initiated on PrEP				
Secondary endpoints				
'Appropriately' on PrEP (based on risk score)				
Partner known HIV status by end of follow-up				
Partner on ART if HIV infected				
TFV-DP levels (median on random sample)				

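### SAP section 5 states no method for analysing HIV incidence, and its GEE comparisons mention neither the six randomisation groups nor a small-sample method for 20 clinics

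*SAP*

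**What the plan says.** SAP section 1 lists "HIV incidence at 9 months postpartum" first under Aim 1a. SAP section 2 makes HIV infection a primary outcome, and SAP section 3 sizes the trial on it: 4% against 2%, 80% power, 10 clinics per arm, 200 women per clinic, "Assuming a coefficient of variation (k) of 0.2".

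In SAP section 5 the Aim 1a paragraph has one comparison, the proportion of enrolled women who use PrEP, which "will be compared between trial arms using GEE with a binomial link". The Aim 1b binary outcomes are handled in the same way. Nothing there concerns HIV incidence. Shell Table 2 in the appendix has an HIV incidence row, a column header "N (%) or incidence/100 py", and a column for a risk ratio with 95% CI and p-value. SAP section 4 adds only that primary analyses are by intention to treat. The protocol has no analysis section that fills the gap.

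On allocation, the randomisation text in SAP section 5 says "each facility was ranked by county and ANC volume and assigned to one of six groups", of 2, 4, 4, 2, 4 and 4 clinics, and then "Representatives from facilities in each group will be asked to select a ball from a bag during the PrIMA training". The same text also says that all allocations balanced on HIV prevalence and ANC volume will be listed and one picked at random. SAP section 3 and the protocol's sample-size section name partner disclosure as a further balancing factor. The group table uses only county and ANC volume.

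**The concern.** The test for the outcome that sets the trial's size is left open until the data are in. Whoever writes the code must choose the model, scale, variance estimator, reference distribution and alpha.

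For the outcomes that do have a method, two features of the design are missing from it. With 20 clusters, an uncorrected sandwich variance with a normal reference tends to reject too often. Leaving out the groups used in the randomisation tends to make a test reject too seldom, and wastes information if the groups predict the outcome. The two effects pull in opposite directions, so the net error rate cannot be read off the plan.

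**Working it through.** **Inputs.** From SAP section 3: 4% vs 2%, k = 0.2, m = 200 women per clinic, 10 clinics per arm, 80% power, PrEP use 20% (targeted) and 5-25% (universal). From the SAP randomisation text: groups of 2, 4, 4, 2, 4, 4. Assumed, because the documents give no figure: two-sided 5%, k = 0.2 carried over to PrEP use, and the share of between-clinic variance that the groups explain (0 to 75%).

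**1. The plan's own figure.** Cluster formula: c = a + (1.960 + 0.842)² × [p0(1−p0)/m + p1(1−p1)/m + k²(p0² + p1²)] / (p0−p1)².
- Bracket: 0.0384/200 + 0.0196/200 + 0.04 × 0.0020 = 0.000192 + 0.000098 + 0.000080 = 0.000370.
- Divided by 0.0004: 0.925. Times 7.849: 7.26.
- With a = 2 (matched or stratified version): 9.26, rounded up to 10, as stated. All seven rows of the table reproduce (27, 15, 12, 10, 9, 8, 6).
- With a = 1 (unstratified version): 8.26, rounded up to 9. No row reproduces.

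The size is therefore consistent with a stratified analysis, which section 5 does not specify.

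**2. Degrees of freedom.** 20 clinics − 6 groups − 1 arm = 13 (critical t 2.160). Arm only: 18 (critical t 2.101).

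**3. Type I error of one assumed default** (arm-only GEE, uncorrected sandwich, normal reference). In closed form, with no group effect: P(|t18| > 1.96 × √(18/20)) = 7.9%. By simulation, 20,000 trials per setting:

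| Share explained by groups | 0% | 25% | 50% | 75% |
|---|---|---|---|---|
| HIV at 4% | 7.7% | 7.4% | 6.6% | 5.7% |
| PrEP use at 20% | 8.0% | 5.8% | 3.9% | 2.3% |

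Adding group terms to the GEE without a correction is worse: P(|t13| > 1.96 × √(13/20)) = 13.8%.

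**4. Type I error of two candidate repairs, at 200 women per clinic.**
- Clinic-level regression on group and arm, t on 13 df: about 5% throughout (4.6-5.3% for HIV at 4% down to 0.5%; 4.6-5.4% for PrEP use with k from 0.1 to 0.5).
- Log-link GEE with group terms, Kauermann-Carroll correction and t on 13 df: 4.4-5.2% for HIV at 4, 2 and 1%, and 4.6-5.2% for PrEP use.
- With very uneven clinic sizes (87-595 or 200-1,363 women) the two separate: 4.0-5.1% for the regression, about 5.5-7.2% for the corrected GEE.

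**5. Power for HIV, 4% vs 2%.** SE = √(0.000370/10) = 0.00608, so the noncentrality is 0.02/0.00608 = 3.29. With no group effect, power is 85.9% on 13 df and 87.5% on 18 df (simulated 86.6% and 88.2%). At a 75% share the simulated figures are 91.4% and 90.1%. With no group effect, simulated power on 13 and 18 df is 78.1% and 80.1% at k = 0.3, and 77.2% and 79.4% for 3% vs 1.5%.

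**6. Power for PrEP use, illustrative 20% vs 25%.** Simulated power on 13 df is 48.8, 55.8, 66.0 and 79.0% as the groups explain 0, 25, 50 and 75%. The arm-only t test on 18 df gives 50.3, 50.6, 52.0 and 53.8%. For 20% vs 10%, SE = √{[(0.16 + 0.09)/200 + 0.04 × 0.05]/10} = 0.0180. The noncentrality is 0.10/0.0180 = 5.5, and power is close to 100% on either df.

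**The case against.** The strongest reply is that the SAP is silent rather than wrong. It names no variance estimator or reference distribution, so no error rate can be attributed to it. GEE is also a sound choice here: with group terms, a correction and 13 df it holds about 5% at the planned equal enrolment. That stands, and the point is therefore about specification. A reader might infer that the planned test runs at 8%; the documents do not support this, because the figure belongs to an assumed default and falls below 5% for PrEP use when the groups matter.

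Three other strong readings also fail.
- That GEE must be replaced because a group with no events makes it undefined. Only that group's intercept diverges. The arm coefficient and its standard error stay finite and equal those from a fit without the group.
- That the trial is underpowered for PrEP use, contrary to the statement that the size "will enable ample statistical power to detect effects on other outcomes". The SAP sets no five-point target and calls its uptake figures speculative. Much of its 5-25% range gives wide contrasts with ample power.
- That the sample size was derived for a stratified analysis. The formula is not stated; the table only fits that version.

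It is also fair that shell Table 2 fixes the form of the HIV result. It does not say how the ratio, interval or p-value is to be obtained. Finally, 13 df rests on separate draws within groups. This is the natural reading, but the text describes two mechanisms. They coincide only if the listed allocations are those that split each of the six groups in half (2 × 6 × 6 × 2 × 6 × 6 = 5,184 of them), and the SAP does not say so.

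**Conclusion.** The point holds as a gap in specification that should be fixed. No method is stated for HIV incidence, and the GEE comparisons leave out the groups and any allowance for 20 clinics. The text alone establishes this, without simulation.

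The size of the consequence depends on two-sided 5%, k = 0.2, 200 women per clinic and an unknown share of variance explained by the groups. Under the assumed default the error runs from about 8% down to about 5-6% for HIV and 2-3% for PrEP use. For HIV, using the groups changes power by −1.6 to +1.3 points, so the benefit is a named test that holds its level. For PrEP use, the rise from about 52% to 66% applies only to the illustrative five-point contrast, with the groups explaining half the variance at a borrowed k.

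**What to change.** In SAP section 5:

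1. State the test for HIV incidence and the alpha. For HIV incidence and the binary arm comparisons, include the six group terms with a small-sample method, by either route:
   - (a) Regression of the 20 untransformed clinic rates or proportions on group and arm, t on 13 df. This holds 5% better if clinic sizes are very uneven. It weights clinics equally, so its risk ratio is a ratio of average clinic rates.
   - (b) Log-link GEE with group terms, Kauermann-Carroll correction and t on 13 df, with fewer df if a group with no events drops out. This stays closer to the method already named.

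   Do not add group terms to a GEE without a correction.
2. State which allocation was used: a draw within each group, one bag for all 20 clinics, or one random pick from the balanced allocations. Match the analysis to it. If one bag was used, the arm-only t test on 18 df is the natural choice: the 13-df test keeps its level, but HIV power falls to 73.6-80.3%, against 88.4-89.0% on 18 df.
3. Reconcile SAP section 3 and the protocol's sample-size section with the randomisation text on partner disclosure.

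The cost is wording and a few lines of code, with no new data. If the groups explain nothing, about 1.5 to 2 points of power are lost against the arm-only t test (HIV 4% vs 2%: about 86-87% against 88%). TFV levels and PrEP duration, measured only in PrEP users, were not examined here.
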